9.4.6 Prior/Concomitant medication/Therapy

Medications will be coded according to the World Health Organization Drug Dictionary (WHO Drug Dictionary, last available version before database lock). Concomitant medications with the IMP will be listed separately by participants.

9.4.7 Efficacy analyses

The efficacy evaluation will be based upon the review of the individual values (graphics), descriptive statistics (summary tables, graphics) and, where applicable, exploratory statistical analysis.

Due to the small sample size and the exploratory characteristics of the study missing or incomplete data of efficacy marker will not be imputed. In case an important number of patients using rescue therapy is observed, visit values removed due to use of rescue therapy will be imputed. The imputation methods applied will be described in an SAP.

9.4.7.1 Description of efficacy variables

Efficacy parameters are described in [Section 8.2](#). The derivation of baseline results is described in [Section 9.4.4.2](#).

The analysis of the efficacy marker will be based on the mITT population. As a sensitivity analysis, the primary endpoint will also be analyzed based on the ITT population. Secondary endpoints analysis might be run on the ITT population as sensitivity analysis in case an important number of patients using rescue therapy is observed.

Sub-analysis might be done for adolescents and adults, if deemed appropriate.

TEWL data collected at the same visit from without and before STS measurement on each of the three spots within the predefined skin areas will be averaged, unless a large difference between spots is observed.

Analysis

Table 4 - Efficacy analyses

Endpoint	Statistical Analysis Methods
Primary	
Percent change from baseline in TEWL after 5 STS assessed on lesional skin at Week 16 in AD patients	
Raw data and change from baseline; ie, absolute and percentage changes, will be summarized with descriptive statistics (such as mean, median, SD, minimum, and maximum) based on the mITT and ITT populations.
 
Profiles for baseline and Week 16 time points will be generated for individual values: eg, spaghetti plot and boxplot, and patients' cohort means.
 
For information purpose as study is not powered (no multiplicity correction will be applied):
 
Difference between baseline and Week 16 values will be tested through one-sided paired t-test at a Type 1 error level of alpha=0.05 ($H_0: 0 \leq TEWL_{Week16} - TEWL_{baseline}$, $H_a: 0 > TEWL_{Week16} - TEWL_{baseline}$).
 
Point estimate, two-sided 90% confidence interval and corresponding one-sided p-value will be reported.
 
If assumption of normal distribution is strongly violated, non-parametric methods: eg, Wilcoxon signed-rank test, will be used; normality assumption will be assessed through quantile-quantile plot and Shapiro-Wilk test at 5% Type I error.

Endpoint	Statistical Analysis Methods
Secondary	
Change (percent and absolute) from baseline in TEWL after 20 STS assessed on lesional skin at Week 16 in AD patients	The similar approach as for the analysis of primary endpoint will be used.
Change (percent and absolute) from baseline in TEWL after 20 STS assessed on non-lesional skin at Week 16 in AD patients	In addition, percentage change relative to the healthy volunteers' cohort will be calculated as a ratio of means by number of STS, at baseline and Week 16 for lesional and non-lesional skin groups.
Change (percent and absolute) from baseline in TEWL after 20 STS assessed on normal skin at Week 16 in HV	
Change (percent and absolute) from baseline in TEWL after 15 STS assessed on lesional skin at Week 16 in AD patients	
Change (percent and absolute) from baseline in TEWL after 15 STS assessed on non-lesional skin at Week 16 in AD patients	
Change (percent and absolute) from baseline in TEWL after 15 STS assessed on normal skin at Week 16 in HV	
Change (percent and absolute) from baseline in TEWL after 10 STS assessed on lesional skin at Week 16 in AD patients	
Change (percent and absolute) from baseline in TEWL after 10 STS assessed on non-lesional skin at Week 16 in AD patients	
Change (percent and absolute) from baseline in TEWL after 10 STS assessed on normal skin at Week 16 in HV	
Absolute change from baseline in TEWL after 5 STS assessed on lesional skin at Week 16 in AD patients	
Change (percent and absolute) from baseline in TEWL after 5 STS assessed on non-lesional skin at Week 16 in AD patients	
Change (percent and absolute) from baseline in TEWL after 5 STS assessed on normal skin at Week 16 in HV	

Endpoint	Statistical Analysis Methods
Change (percent and absolute) from baseline in TEWL before STS on lesional skin in AD patients over time	Raw data and change from baseline; ie, absolute and percentage changes, will be summarized with descriptive statistics (such as mean, median, SD, minimum, and maximum) by groups, number of STS and time point.
Change (percent and absolute) from baseline in TEWL before STS on non-lesional skin in AD patients over time	Profiles over study days will be generated for individual values and group means for raw data and absolute change from baseline.
Change (percent and absolute) from baseline in TEWL before STS on normal skin in healthy volunteers over time	Percentage change relative to the healthy volunteers' cohort will be calculated as a ratio of means by number of STS and time point for lesional and non-lesional skins groups.
Change (percent and absolute) from baseline in TEWL after STS assessed on lesional skin in AD patients over time	As exploratory analysis time to improvement of skin barrier function for lesional and non-lesional skin area measured by TEWL will be summarized. Improvement is defined as time to the first post-baseline day for which at least one TEWL measure of a patient is equal or lower than the median, of the corresponding TEWL measured in his/her matched healthy volunteer over time. Results might be reported through Kaplan-Meier plot.
Change (percent and absolute) from baseline in TEWL after STS assessed on non-lesional skin in AD patients over time	
Change (percent and absolute) from baseline in TEWL after STS assessed on normal skin in healthy volunteers over time	
Change (percent and absolute) in TEWL area under the curve (TEWL AUC: a composite measure before and after 5, 10, 15 and 20 STS) for skin barrier function in lesional skin in AD patients over time	As all TEWL values are expected to be positive, area under the TEWL curve will be calculated using the trapezoidal method over the 10 or 20 STS (measurement at every five STS) at each visit.
Change (percent and absolute) in TEWL area under the curve (TEWL AUC: a composite measure before and after 5, 10, 15, and 20 STS) for skin barrier function in non-lesional skin in AD patients over time	Raw data and change from baseline; ie, absolute and percentage changes, will be summarized with descriptive statistics (such as mean, median, SD, minimum, and maximum) by groups and time points.
Change (percent and absolute) in TEWL area under the curve (TEWL AUC: a composite measure before and after 5, 10, 15, and 20 STS) for skin barrier function in normal skin in healthy volunteers over time	Profiles over study days will be generated for individual values and group means for raw data and absolute change from baseline.
	Percentage change relative to the healthy volunteers' cohort will be calculated as a ratio of means by time point for lesional and non-lesional skins groups.
	As exploratory analysis time to improvement of skin barrier function for lesional and non-lesional skin area measured by TEWL AUC will be summarized. Improvement is defined as time to the first post-baseline day for which TEWL AUC of a patient is equal or lower than the median, of the corresponding TEWL AUC computed in his/her matched healthy volunteer over time. Results might be reported through Kaplan-Meier plot.
Tertiary/exploratory	
Change (percent and absolute) in lipidomics parameters in lesional and non-lesional skin including the ratio of EOS CER and NS CER, and FLG breakdown products of UCA and PCA concentrations at Week 8 and Week 16, respectively	Lipidomics data will be summarized with descriptive statistics. Multivariate unsupervised and supervised analyses will be performed as appropriate.
Global characterization of protein-bound ceramides over time	

Endpoint	Statistical Analysis Methods
Changes (percent and absolute) in the expression of proteins associated with skin barrier function including keratin intermediate filaments, proteins associated with inflammatory response, and glycolysis and oxidative stress response proteins in STS protein extracts over time.	Proteomics data will be summarized with descriptive statistics. Multivariate unsupervised and supervised analyses will be performed as appropriate.
Changes in expression of genes associated with epidermal differentiation, barrier and lipid metabolism, and Type 2 inflammation over time.	Skin transcriptome phenotype data will be summarized with descriptive statistics. Multivariate unsupervised and supervised analyses will be performed as appropriate.

Change (percent and absolute) from baseline in EASI over time
 
Change (percent and absolute) from baseline in SCORAD over time
 
Change (percent and absolute) from baseline in ISS over time
 
Change (percent and absolute) from baseline in POEM over time
 
Change (percent and absolute) from baseline in DLQI in patients 18 years of age and CDLQI in patients ≥ 12 and < 18 years of age over time
 
Change (percent and absolute) from baseline in peak pruritus NRS over time
 
Change (percent and absolute) from baseline in quality of sleep NRS over time
 
Change (percent and absolute) from baseline in photograph outputs (eg, severity score) obtained from skin imaging over time
	
EASI, SCORAD, POEM, DLQI/CDLQI, peak pruritus NRS, and quality of sleep NRS, photograph outputs:
 
 • Raw data and change from baseline; ie, absolute and percentage changes, will be summarized with descriptive statistics (such as mean, median, SD, minimum, and maximum) by time points based on patients from mITT population. • Mean plots (mean \pm SEM) on raw data and absolute change from baseline over time for patients' cohort will be produced. 
ISS:
 
 • Number and percentage of patients by severity will be reported by time points based on the patients from mITT population. • Barplot (percentages of patients by severity grade) over time for patients' cohort will be produced.

Correlation between baseline values of TEWL before STS and TEWL AUC in lesional and non-lesional skin of AD patients with the following baseline measures:
 
 • Local target lesion erythema and edema/papulations; ISS • EASI, SCORAD • POEM, DLQI, CDLQI, peak pruritus NRS, and quality of sleep NRS • Lipidomics in STS (ratio of EOS CER to NS CER) • FLG breakdown products of UCA and PCA concentrations in STS • Key components of skin proteomics in STS (expression of proteins associated with skin barrier function) • Key components of gene expression from transcriptomics • Image-derived severity score in targeted lesional skin 	
Scatterplot to visualize the form of the relationship between variables will be produced for patients' cohort at specific time points: ie, baseline, Week 8 and Week 16, based on the mITT population.
 
Pearson correlation will be assessed at each defined time points for EASI, SCORAD, POEM, DLQI/CDLQI, peak pruritus NRS, quality of sleep NRS, and photograph outputs. Pearson correlation coefficient and p-value will be reported.
 
Spearman's rank correlation will be assessed at each defined time points for ISS. Spearman correlation coefficient and p-value will be reported.
 
As exploratory analysis repeated measures correlation method might be used to assess the overall correlation pooling data from baseline, Week 8 and Week 16 (34).

Endpoint	Statistical Analysis Methods
Correlation between percent change from baseline in TEWL before STS and TEWL AUC in lesional and non-lesional skin of AD patients at Week 8 and Week 16 with corresponding change from baseline in the following measures:	
• Local target lesion erythema and edema/papulations; ISS• EASI, SCORAD• POEM, DLQI, CDLQI, peak pruritus NRS, and quality of sleep NRS• Lipidomics in STS (ratio of EOS CER to NS CER)• FLG breakdown products of UCA and PCA concentrations in STS• Key components of skin proteomics in STS (expression of proteins associated with skin barrier function)• Key components of gene expression from transcriptomics• Image-derived severity score in targeted lesional skin

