Lesional and non-lesional skin areas for TEWL assessment and STS will be identified on the upper limbs or lower limbs at baseline ("predefined skin area"). TEWL and STS-assessment at pre-defined non-lesional (normal looking) skin area in AD patients should be made about 4 cm from the edge of the lesional area.

Within the predefined lesional skin (LS) and non-lesional skin (non-LS) areas three closely adjacent spots will be identified for subsequent skin barrier function assessment (3 spots on lesional skin, 3 spots on non-lesional skin). These spots must not overlap with each other once skin tapes are applied.

The skin barrier function without and before STS will be assessed using TEWL measurement on each of the three spots within these pre-defined skin areas at each visit.

Repeated TEWL assessment in pre-defined lesional and non-lesional skin areas of AD patients after STS for lipidomics, proteomics and transcriptomics analysis in STS samples will be conducted at baseline (Week 0, Day 1), Week 2 (Day 15), Week 4 (Day 29), Week 8 (Day 57), Week, 12 (Day 85), and at EoT at Week 16 (Day 113).

In order to allow the skin to recover from the STS, the skin barrier function assessment with STS will be performed as follows: STS assessment on baseline (Week 0), Week 8 and Week 16 will be conducted on the first spot within the predefined lesional and non-lesional skin area. STS assessment on Week 2 will be conducted on the second spot. STS assessment on Week 4 and Week 12 will be conducted on the third spot.

TEWL will be measured before and after 5, 10, 15, and 20 STS (5 TEWL assessments per visit) on targeted, predefined lesional, non-lesional skin in AD patients at baseline, Week 2, Week 4, Week 8, Week 12, and Week 16 on the predefined first, second or third spot, respectively.

Skin barrier function in approximately twenty healthy volunteers matched for age, gender, location of targeted lesion area, and study site to the AD cases will be assessed in a similar manner at baseline, twice a week during the first two weeks, once a week during Week 3 to Week 4, every two weeks from Week 4 to Week 8, and every four weeks up to Week 16 thereafter, serving as a reference comparator for skin barrier function.

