- g* Peak pruritus NRS and quality of sleep NRS will be assessed daily from Day-7 to Day -1; daily from Day 1 to Day 29 and then for the 7 days prior to Week 6, Week 8, to Week 12 and to Week 16 by e-diary. Patients will bring the eDiary to the site at each visit. eDiary will be reviewed for any questionnaires omission and dispensed back to patients at each visit.
- h* TEWL to be conducted before STS and then after 5, 10, 15, and 20 STS in pre-defined lesional and non-lesional skin. All skin tape strips will be collected and stored.
- i* At Week 0, 8 and 16 STS will be conducted on the first spot within the predefined skin area. At Week 2 STS will be conducted on the second spot within the predefined skin area. At Week 4 and 12 STS will be conducted on the third spot within the predefined skin area. TEWL will be assessed in lesional and non-lesional skin before STS and after 5, 10, 15, and 20 STS. All skin tape strips will be collected and stored for lipidomics, proteomics, and transcriptomics analyses.
- j* Emollients should NOT be applied from Day -7 to the EoT (Week 16, Day 113) to the targeted, pre-defined skin areas that will be used for TEWL assessment. Participants should not take showers or soaking in a bathtub within 6 hours before TEWL assessment. Compliance must be documented in participant's source data. Emollients for use during the study will be provided by the study site to study participants. Use of emollients should be documented in a diary.
- k* Limited to skin-related physical examination at baseline and EoT visit.
- l* Pre-defined lesional (3 spots) and non-lesional skin areas (3 spots), whereby the assessment spots on non-lesional skin are located about 4 cm apart from the edge of the AD lesion.
- m* TEWL will be measured at each of the three closely adjacent spots within the predefined skin areas at all visits as baseline assessment; if there is STS, subsequent TEWL assessment will only be done at the lesional and no-lesional spot, at which STS is performed.
- n* In case STS assessment is to be conducted at an unscheduled visit or at a premature end of treatment visit the assessment should be conducted at that spot of the skin area, for which the period passed since the last STS assessment is the longest.

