
 Evaluate time course of improvement in skin barrier function with TEWL assessed before and after STS in pre-defined lesional and non-lesional skin in patients with moderate to severe AD treated with dupilumab in reference to normal skin of healthy volunteers. 	
 Change (percent and absolute) from baseline in TEWL before STS on lesional skin in AD patients over time. Change (percent and absolute) from baseline in TEWL before STS on non-lesional skin in AD patients over time. Change (percent and absolute) from baseline in TEWL before STS on normal skin in healthy volunteers over time. Change (percent and absolute) in TEWL area under the curve (TEWL AUC: a composite measure before and after 5, 10, 15 and 20 STS) for skin barrier function in lesional skin in AD patients over time. Change (percent and absolute) in TEWL AUC (a composite measure before and after 5, 10, 15, and 20 STS) for skin barrier function in non-lesional skin in AD patients over time. Change (percent and absolute) in TEWL AUC (a composite measure before and after 5, 10, 15, and 20 STS) for skin barrier function in normal skin in healthy volunteers over time. Change (percent and absolute) from baseline in TEWL after STS assessed on lesional skin in AD patients over time. Change (percent and absolute) from baseline in TEWL after STS assessed on non-lesional skin in AD patients over time. Change (percent and absolute) from baseline in TEWL after STS assessed on normal skin in healthy volunteers over time.
Tertiary/exploratory	

 Evaluate dupilumab treatment effect on skin lipidomics using STS samples in both pre-defined lesional and non-lesional skin in patients with moderate to severe AD in reference to normal skin of healthy volunteers. 	
 Changes (percent and absolute) in lipidomics parameters in lesional and non-lesional skin including the ratio of EOS CER and NS CER, and FLG breakdown products of UCA and PCA concentrations at Week 8 and Week 16, respectively. Global characterization of protein-bound ceramides over time.

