8.2 EFFICACY ASSESSMENTS

8.2.1 Transepidermal water loss assessment and skin tape stripping

8.2.1.1 Transepidermal water loss assessment

Transepidermal water loss is a skin barrier function test that measures perspiration or water loss through the skin. Transepidermal water loss is generally higher in AD skin compared to normal skin as the barrier is disrupted allowing water to evaporate more readily. If the barrier improves with dupilumab treatment, TEWL would be expected to decrease.

TEWL assessment will be conducted in a quiet environment with temperature and humidity being documented. TEWL measurements will be conducted in the same room throughout the study where possible. Subjects will be acclimated to the room for a minimum of 20 minutes prior to TEWL measurements. Room temperature will be set to be within 19.0°C to 23.0°C. Humidity will be set to be below 60% as the maximum allowed humidity. To further control TEWL readout, moisturizers will be standardized for all study participants starting from Day -7 until Day 113 (Week 16). The first TEWL assessment at each visit will be conducted at each of the three spots in predefined lesional and non-lesional areas respectively. After start of STS all subsequent TEWL assessments at each visit will be done on the single lesional and non-lesional spot respectively at which the STS is performed (see also [Figure 3](#)).

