8.2.1.2 Skin tape stripping and collection of skin tapes

In addition to TEWL measurements at the skin surface, TEWL measurements can be combined with STS to measure skin barrier function. With STS, the uppermost layers of the skin are peeled away using adhesive discs. Skin with compromised skin barrier exhibits greater changes in TEWL. The area under the curve for TEWL measurements over a defined number of STS reflects the overall function of the SC.

This procedure involves the defined, non-invasive application of a commercially available adhesive sheet on the surface of the skin at predefined areas. A dedicated instrument (eg, D-SQUAME Pressure Instrument D500) is used to apply a defined pressure onto the skin tape strip for 5 to 10 seconds. Thereafter the skin tape strip will be peeled off the skin in a ripping motion using a forceps (= the skin tape-stripping method).

This procedure will be repeated up to 20 times sequentially, interrupted every 5 STS by TEWL to collect samples from the stratum corneum. The samples will be collected for lipidomics, proteomics and transcriptomics assessment.

[figure not shown]
Lesional and non-lesional areas of skin will be tested. Patients will undergo skin barrier function tests at time points according to [Section 1.3](#) before, and after skin tape stripping.

Healthy volunteers will undergo skin barrier function tests at time points according to [Section 1.4](#) before, and after skin tape stripping.

Specifically, lipidomic, proteomic and transcriptomics samples will be collected by STS at baseline, Week 2, 4, 8, 12, and 16. A total 240 skin tapes will be collected in lesional, non-lesional or normal skin, respectively.

[figure not shown]
In order to allow the skin to recover from STS three closely adjacent spots (without an overlap for the skin tapes) will be identified for subsequent skin barrier function assessment within lesional, non-lesional and normal skin area ([Figure 2](#)). STS assessments from the same spot will be separated by 8 weeks. In case of STS assessment at an unscheduled visit or at a premature end of treatment visit the assessment should be conducted at that spot of the skin area, for which the time period passed since the last STS assessment is the longest.

Figure 2 - Example of selection of skin spots within lesional and non-lesional skin

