9.4.4.2 Baseline efficacy parameters

Baseline is defined as the last available and evaluable value before and closest to the first dose of the IMP: ie, at D1 (V02, W0), for patients and as the last available and evaluable value at D1 (V02, W0) for healthy volunteers. For TEWL data, the average of the values of the 3 spots within each predefined skin area will be used as baseline, unless a large difference between the spots is observed.

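### The default three-spot mean of pre-stripping TEWL compares an unstripped Day 1 with early visits that include recently stripped spots, and no planned analysis separates them

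*Protocol*

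**What the plan says.** Protocol 8.2.1.1 states: "The first TEWL assessment at each visit will be conducted at each of the three spots in predefined lesional and non-lesional areas respectively". Footnote m of the patients' schedule (Section 1.3) repeats this for every visit, and footnote h of Section 1.4 does the same for healthy volunteers.

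The readings are then pooled. For baseline, Section 9.4.4.2 says "the average of the values of the 3 spots within each predefined skin area will be used as baseline". For each visit, Section 9.4.7.1 has the same default for the readings: "without and before STS measurement on each of the three spots within the predefined skin areas will be averaged". It allows one exception, worded "unless a large difference between spots is observed", and attaches no threshold or replacement rule to it.

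Stripping rotates over the spots on the same schedule in both cohorts: spot 1 at Weeks 0, 8 and 16, spot 2 at Week 2, spot 3 at Weeks 4 and 12. The synopsis gives the purpose: "In order to allow the skin to recover from the STS, the skin barrier function assessment with STS will be performed as follows". Section 8.2.1.2 adds: "STS assessments from the same spot will be separated by 8 weeks".

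Table 4 summarises TEWL over time by group, number of strips and time point. SAP Section 1.2 defines change from baseline by matching the number of strips on Day 1.

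**The concern.** The rotation protects a spot from being stripped again too soon. It does not keep a recently stripped spot out of the pre-STS mean. Day 1 values come before any study stripping; later values do not. Matching on number of strips does not restore a like-for-like comparison, because a pre-STS reading counts as zero strips whether its spot is untouched or had 20 strips three days before.

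The endpoint at stake is the secondary objective that Table 1 words as "Evaluate time course of improvement in skin barrier function with TEWL assessed before and after STS". Pre-STS TEWL is the only TEWL at five of the ten post-baseline visits (Days 4, 8, 11, 22 and 43), so it carries much of the early curve. If stripped spots still read high, the patients' early change from baseline would look smaller than it is.

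**Working it through.** **Inputs.** Stripping days (Protocol 1.3 footnote i; 1.4 footnote e): spot 1 on D1, D57, D113; spot 2 on D15; spot 3 on D29, D85. Visit days are from the schedules. At a stripping visit, the pre-STS reading comes before that day's strips.

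**The plan's own figure.** Spot 1: 57 − 1 = 56 and 113 − 57 = 56 days. Spot 3: 85 − 29 = 56 days. Spot 2 is stripped once. The stated 8 weeks is reproduced.

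**Nominal days since last stripping** (visit day minus latest earlier stripping day on that spot; – means never stripped):

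| Visit | Post-STS TEWL too? | Spot 1 | Spot 2 | Spot 3 | Stripped spots in mean |
|---|---|---|---|---|---|
| D1 | yes | – | – | – | 0 |
| D4 | no | 3 | – | – | 1 |
| D8 | no | 7 | – | – | 1 |
| D11 | no | 10 | – | – | 1 |
| D15 | yes | 14 | – | – | 1 |
| D22 | no | 21 | 7 | – | 2 |
| D29 | yes | 28 | 14 | – | 2 |
| D43 | no | 42 | 28 | 14 | 3 |
| D57 | yes | 56 | 42 | 28 | 3 |
| D85 | yes | 28 | 70 | 56 | 3 |
| D113 | yes | 56 | 98 | 28 | 3 |

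Visit windows widen these: spot 1 at D4 is 1 to 5 days from stripping, and spot 2 at D22 is 3 to 11 days.

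**Illustrated size.** Suppose the spots share the same true level and m of the three read a fraction r too high (r is assumed). The mean rises by m·r/3, and a true 20% fall reads as 0.8 × (1 + m·r/3) − 1.

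- m = 1: r = 10% gives 0.8 × 1.0333 − 1 = −17.3%; r = 20% gives −14.7%; r = 30% gives 0.8 × 1.10 − 1 = −12.0%.
- m = 2, same r: −14.7%, −9.3% and −4.0%. This needs an effect lasting 21 days at D22 or 28 days at D29.

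An effect lasting 28 days would also reach D57, D85 and D113, each of which has one spot at exactly 28 days.

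**If the effect decays.** With r starting at an assumed 30% and halving every 5 days, the D4 mean rises by 0.30 × 2^(−3/5)/3 = 6.6%. At D8 the rise is 3.8%. At D22 it is 0.30 × (2^(−7/5) + 2^(−21/5))/3 = 4.3%, and from D29 onward it is 1.7% or less.

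**Ratio to volunteers.** With elevation r_p in patients and r_h in volunteers, the ratio of means is multiplied by (1 + m·r_p/3)/(1 + m·r_h/3). This is 1 only if r_p = r_h. For m = 1, r_p = 30% and r_h = 10% (both assumed), it is 1.10/1.0333 = 1.065.

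**The case against.** The strongest reply is that no effect has been shown. The only statement on how skin settles after stripping is in Protocol 2.3.1, which expects mild erythema to clear within 12 hours. That concerns erythema, not TEWL, so it does not close the question, but nothing in the documents shows a lasting TEWL rise. A decaying effect would also be small by D29. Both points stand, and they limit the priority.

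There are safeguards. Volunteers follow the same spot schedule, their pre-STS change is an endpoint, the ratio to them is taken at each time point, and individual profiles are plotted. These may reveal an artefact. They do not correct the patients' own curve, and the ratio cancels the effect only if both cohorts respond and recover alike. Section 3.1 says that healthy skin is not very sensitive to stripping while disrupted skin shows larger TEWL changes, so equal response cannot be taken for granted.

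The averaging exception might catch a large carry-over up to D29, where stripped and unstripped spots coexist. It has no threshold, would pass a moderate effect, and on D43 no unstripped spot remains.

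A reader might also infer that time to improvement is made too easy, because stripping raises the matched volunteer's median. The same statement about healthy skin makes a large volunteer rise less plausible. That analysis is labelled exploratory and also counts post-STS readings, so the documents do not establish this bias.

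**Conclusion.** The schedule arithmetic is exact and the gap is real: by default, the early pre-STS means mix stripping histories that Day 1 does not have, and no planned analysis separates them. The direction of any bias in the patients' change from Day 1 is toward less improvement. Its size is unknown and may be zero; the 17.3 to 12.0% range rests on an assumed 10 to 30% elevation in one spot.

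Three stronger readings are not supported:

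- The early curve is not shown to be biased; the plan only leaves it open to bias.
- The 8 weeks is a spacing rule for repeat stripping, not a stated TEWL recovery time, so a spot under 56 days cannot be called unrecovered.
- The primary and post-STS endpoints are not affected by this averaging: post-STS readings come from a single spot, and the SAP compares them with Day 1 at the same number of strips.

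From D57 the most recent stripping is 28 nominal days old. Whether those visits are affected depends on the same unknown duration, so they should not be assumed clean if a 28-day effect is entertained at D29. The study reference manual, which holds the detailed procedure, was not available. This is a cheap improvement of low to moderate priority in an exploratory study.

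**What to change.** Keep the three-spot mean as planned, and add the following to the SAP for all three groups:

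- **D4 to D29:** a sensitivity analysis of pre-STS TEWL on never-stripped spots only (spots 2 and 3 on D4–D15, spot 3 on D22–D29), each compared with the Day 1 value of the same spots.
- **D43 and later:** spot-level values shown by time since stripping, because no unstripped spot remains.
- **Time to improvement:** where the exploratory pre-STS analysis is reported, repeat it on the D4–D29 basis.

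Retain the large-difference exception; it also covers differences unrelated to stripping, such as uneven lesions or a faulty reading.

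The cost is SAP wording and analysis time; every spot is already measured. The main downside is noise. With equal spot variances and between-spot correlation ρ, the SD of a k-spot mean relative to three spots is √(f(k)/f(3)), where f(k) = (1 + (k − 1)ρ)/k. For ρ = 0.7 (assumed), two spots give √(0.85/0.80) = 1.03 and one gives √(1/0.80) = 1.12. For ρ = 0 they give 1.22 and 1.73. So the SD rises 3 to 22% with two spots and 12 to 73% with one.

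The spot set also drops from two to one between D15 and D22, so its baselines need labels and any step there needs care. The analysis further assumes that stripping one spot does not affect its close neighbours.
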